#### **6.2 Secondary Objectives**

- To evaluate the efficacy of treatment with VX-371 in HS compared with placebo in subjects with CF who are  $\geq 12$  years of age, homozygous for the *F508del-CFTR* mutation, and being treated with Orkambi
- To evaluate the efficacy of treatment with VX-371 in HS compared with VX-371 in placebo in subjects with CF who are  $\geq 12$  years of age, homozygous for the *F508del-CFTR* mutation, and being treated with Orkambi

- To evaluate the efficacy of treatment with VX-371 in placebo compared with placebo in subjects with CF who are  $\geq 12$  years of age, homozygous for the *F508del-CFTR* mutation, and being treated with Orkambi
- To investigate the pharmacokinetics (PK) of VX-371 in subjects with CF who are  $\geq 12$  years of age, homozygous for the *F508del-CFTR* mutation, and being treated with Orkambi

[figure not shown]

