### **Maintenance of Stable Medication Regimen for CF:**

It is recommended that subjects remain on stable CF medication regimens from 28 days before Day 1 through the Safety Follow-up Telephone Contact with the exception of those subjects taking HS. Those subjects taking HS before the Screening Period will washout from HS during the Run-in Period from Day -28 to Day -1 and will not be allowed to take HS for through the Safety Follow-up Telephone Contact or Safety Follow-up Visit (other than as blinded inhaled study drug if allocated to a relevant treatment sequence). A stable medication regimen is defined as the current medication regimen that subjects have been following for at least 28 days before Day 1. Subjects are to be on stable CF medication (including Orkambi) for at least 28 days before dosing with inhaled study drug on Day 1.

Specific requirements apply to certain CF medications:

- Subjects must be on a stable regimen of lumacaftor/ivacaftor for a minimum of 28 days of treatment before the Day 1 Visit and continue this through the Safety Follow-up Telephone Contact.
- Subjects who are on a stable regimen of a single inhaled antibiotic that is continuously administered should remain on this antibiotic through the Safety Follow-up Telephone Contact.
- Subjects who are on a stable regimen of a single inhaled cycling antibiotic (e.g., Tobramycin Inhalation Solution [TOBI®] regimen) should remain on this antibiotic through the Safety Follow-up Telephone Contact. Inhaled cycling antibiotics should be administered in 28-day-on/28-day-off cycles.

Clinic visits on Day 1 and Day 57 should be timed to occur **exactly** at the start of an on-cycle; treatment during the on-cycle should then end after **no more than** 28 days.

- At the time of study entry, subjects who are on an alternating regimen of inhaled cycling antibiotics that comprise continuous administration of antibiotics (e.g., TOBI administration alternating with Cayston®) should remain on these antibiotics according to their alternating regimens through the Safety Follow-up Telephone Contact.

The first dose of inhaled study drug in each Treatment Period should coincide **exactly** with the first dose of the same cycled inhaled antibiotic (e.g., if TOBI is being administered first and Cayston second in the cycle, the Day 1 and Day 57 Visit should coincide with the first dose of TOBI).

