## **8.2           Rationale for Study Design and Study Drug Regimens**

### **8.2.1       Study Design**

This Phase 2a, randomized, double-blind, placebo-controlled, incomplete block, crossover, multicenter study in subjects  $\geq 12$  years of age with CF who are homozygous for the *F508del-CFTR* mutation and receiving stable Orkambi treatment is designed to evaluate the safety, efficacy, and PK of treatment with VX-371 in 4.2% HS compared to 4.2% HS alone.

A randomized, double-blind, placebo-controlled study design was selected to avoid observer bias and reduce symptoms or outcomes arising from the investigator's or the subject's knowledge of treatment. A crossover design in which subjects are randomized to 1 of 4 treatment sequences will enable within-subject comparison of selected treatment effects with increased statistical power. A 28-day washout period is judged to be of sufficient duration for all subjects to return to their baseline values for FEV1 and to accommodate synchronization with cycling inhaled antibiotics.

There are 2 primary endpoints; the first is to evaluate safety and tolerability, and the second is to evaluate efficacy as measured by the absolute change in ppFEV1 from study baseline at Day 28 in each Treatment Period. Although the primary objectives are to evaluate the safety and efficacy of VX-371 in 4.2% HS versus 4.2% HS alone, 2 additional treatment sequences will compare VX-371 in 0.17% saline (placebo) versus 0.17% saline (placebo). These comparisons will provide insight with respect to the effect of VX-371 alone and inform design options for future studies. Even though 2 different concentrations of saline will be used, the double-blind will be maintained with respect to VX-371 because allocation to this component will remain unknown to both investigators and subjects.

A sample size of approximately 150 subjects is considered feasible and is expected to provide sufficient data to evaluate the efficacy, safety, and PK of VX-371 formulated with and without HS. The unbalanced randomization ratio permits more subjects to be used to address the primary study objective.

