#### **12.1           Sample Size and Power**

The primary efficacy endpoint is the absolute change in ppFEV1 from study baseline to the Day 28 measurements in each Treatment Period.

The null hypothesis to be tested is that the mean change from study baseline in ppFEV1 to the Day 28 measurements is the same for VX-371 in combination with HS versus HS alone.

To have a feasible sample size and study duration, this study uses a crossover design. Assuming a standard deviation (SD) of 7 percentage points, 50 subjects per sequence are needed to have an approximately 81% power to detect a 3 percentage point treatment difference in the mean absolute change in ppFEV1 from study baseline at Day 28 between VX-371 + HS and HS alone. The study will have an approximately 80% power to detect a 3 percentage point (within treatment) change from baseline at Day 28 in ppFEV1 for VX-371. A 2-sided significance level of 0.05 was used in the sample size calculations. The sample size also takes into consideration an assumed dropout rate of 10%.

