## 7.2 Sample Size and Power

The primary efficacy endpoint is the absolute change in ppFEV1 from study baseline to the Day 28 measurements in each Treatment Period.

The null hypothesis to be tested is that the mean change from study baseline in ppFEV1 to the Day 28 measurements is the same for VX-371 in combination with HS versus HS alone.

To have a feasible sample size and study duration, this study uses a crossover design. Assuming a standard deviation (SD) of 7 percentage points, 50 subjects per sequence (VX-371 + 4.2% HS followed by 4.2% HS; 4.2% HS followed by VX-371 + 4.2% HS) are needed to have approximately 81% power to detect a 3 percentage point treatment difference in the mean absolute change in ppFEV1 from study baseline at Day 28 between VX-371 + HS and HS alone. The study will have approximately 80% power to detect a 3 percentage point (within treatment) change from study baseline at Day 28 in ppFEV1 for VX-371. A 2-sided significance level of 0.05 was used in the sample size calculations. The sample size took into account an assumed dropout rate of 10%.

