##### **9.3.1.2 Primary Analysis of Primary Efficacy Endpoint**

The null hypothesis to be tested is that the mean change from study baseline in ppFEV1 at Day 28 is the same for VX-371 with HS versus HS alone.

[figure not shown]
The primary analysis of the primary efficacy endpoint will be based on a mixed-effects model. This model will include the absolute change from study baseline in ppFEV1 at Day 28 as the dependent variable and the following fixed effects: treatment, period and ppFEV1 at study baseline and subject as a random effect. The within-subject covariance will be assumed to have the compound symmetry (CS) structure. Denominator degrees of freedom for the F-test for fixed effects will be estimated using the Kenward-Roger approximation.

[figure not shown]
No imputation of missing data will be performed. Subjects who have data only for one of the periods will have a data structure similar to a parallel-group trial. Assuming that these subjects have dropped out at random, an estimate of treatment effect based on such subjects will be combined with the estimate from subjects who have data in both treatment periods with weights based on the precision of these estimates.

[figure not shown]

[figure not shown]
where “primary efficacy endpoint” is the absolute change from study baseline in ppFEV1 at day 28.

[figure not shown]
Descriptive summary statistics including n, mean, SD, and least-square means (LS means), along with its SE, 95% CI and the within-treatment 2-sided *P* value will be provided by treatment group. The between-treatment LS mean differences [VX-371 + HS versus HS, VX-371 + HS versus VX-371 + placebo, VX-371 + HS versus placebo, and VX-371 + placebo versus placebo] with the corresponding SE, 95% CIs and 2-sided *P* values will be presented. The cumulative distribution of the absolute change from study baseline in ppFEV1 at Day 28 will be plotted by treatment group.

[figure not shown]

[figure not shown]

[figure not shown]

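### Does the 80% power stated for VX-371 hide a placebo comparison that has only about 51%?

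*Protocol*

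**What the plan says.** Protocol 12.1 sizes the trial on VX-371 + HS versus HS: "Assuming a standard deviation (SD) of 7 percentage points, 50 subjects per sequence are needed" for about 81% power to detect a 3-point difference in change in ppFEV1 at Day 28, allowing for 10% dropout. "A 2-sided significance level of 0.05 was used in the sample size calculations". A second figure follows: "The study will have an approximately 80% power to detect a 3 percentage point (within treatment) change from baseline at Day 28", for VX-371. SAP 7.2 has the same claim, "approximately 80% power to detect a 3 percentage point (within treatment) change from study baseline at Day 28", and the Synopsis carries it too.

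Protocol 6.2 lists as a secondary objective: "To evaluate the efficacy of treatment with VX-371 in placebo compared with placebo in subjects with CF". Sequences 3 and 4, which serve that comparison, hold 25 subjects each against 50 each in sequences 1 and 2 (Protocol Table 8-1). Protocol 8.2.1 says that a total of about 150 subjects "is expected to provide sufficient data to evaluate the efficacy, safety, and PK of VX-371 formulated with and without HS". It also explains that the unequal ratio puts more subjects on the primary question, and that the VX-371-alone sequences are there for insight and to guide later studies.

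SAP 9.3.1.2 gives LS means for each treatment "along with its SE, 95% CI and the within-treatment 2-sided" P value. It also gives between-treatment differences, including VX-371 + placebo versus placebo, each with SE, 95% CI and P value. SAP 9.3.4 applies no multiplicity adjustment.

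**The concern.** The 80% comes straight after the 81% for a controlled comparison and is the only power attached to VX-371 itself. A reader in a hurry could take it as the chance of showing a 3-point benefit of VX-371 over placebo. It is not: a change from baseline within one treatment has no comparator and is not among the listed objectives.

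The controlled comparison has half the subjects of the primary one, so its power must be well below 81%. At about 51%, a true 3-point effect would be missed roughly half the time, and the sentence about sufficient data with and without HS would look generous.

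A within-treatment P value can also be significant when the drug does nothing, because anything that moves ppFEV1 over 28 days counts towards it. The protocol contains one candidate. For subjects on a single cycling inhaled antibiotic, the Day 1 and Day 57 visits are to fall exactly "at the start of an on-cycle; treatment during the on-cycle should then end after" no more than 28 days. Study baseline then follows an off-cycle and Day 28 comes at the end of an on-cycle, in every arm.

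**Working it through.** **Inputs.** Two-sided alpha 0.05, SD 7, difference 3 and dropout 10% (Protocol 12.1); 100 subjects in sequences 1 and 2, 50 in sequences 3 and 4 (Table 8-1). Completers: 100 × 0.9 = 90 and 50 × 0.9 = 45. The 3-point effect for the placebo comparison is carried over from the primary one, because the documents give no separate value. Power is from the noncentral t distribution.

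**The plan's 81%.** Take 7 as the SD of one change, with no correlation between periods. The SD of the within-subject difference is 7 × √2 = 9.90. SE = 9.90/√90 = 1.04, noncentrality 3/1.04 = 2.87, df 88: power 81.2%. Other readings do not fit. If 7 is the SD of the within-subject difference, power is 98.0%; with no dropout it is 85.1%.

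**The plan's 80%.** One-sample test, SD 7, n = 45: SE = 7/√45 = 1.04, df 44, power 80.3%. With n = 90 and SD 7 it would be 98.0%, so at the stated SD the figure belongs to the VX-371 + placebo treatment. The SE equals that of the primary comparison, because 7√(2/90) = 7/√45. That is why the two stated powers are so close.

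**The unstated power, VX-371 + placebo versus placebo.** Same SD of the difference, 45 completers: SE = 9.90/√45 = 1.48, noncentrality 3/1.48 = 2.03, df 43: power 51.1%. With error df pooled over all four sequences (about 132) it is 52.3%; if all 50 complete, 55.6%. The 95% CI half-width is about 2.98 points, and 80% power is reached at about 4.2 points. Reaching 80% for 3 points would take 88 completers, or 98 randomized, instead of 50.

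The step from 81% to 51% does not depend on what the SD of 7 means. Solving for the SD of the difference that gives exactly 81% yields 9.92 at n = 90, and then 50.9% at n = 45. At n = 100 it yields 10.47, and then 51.0% at n = 50.

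**Effect of between-period correlation** (assumed, since the documents give none; 7 is the SD of change):

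| Correlation | Primary, n = 90 | VX-371 + placebo vs placebo, n = 45 |
|---|---|---|
| 0 | 81% | 51% |
| 0.1 | 85% | 55% |
| 0.25 | 91% | 63% |
| 0.5 | 98% | 80% |

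**The case for a change.** The strongest case for acting is that the gap is real and cheap to close. A listed secondary objective gets a P value and no stated power. At the variance behind the plan's own 81%, that power is about one in two, and a favourable correlation cannot be claimed for this comparison alone, since it would lift the primary above 81% as well. Nor is 51% a floor: Protocol 8.1 lets the sponsor stop enrolling in these two sequences and run every analysis anyway. The within-treatment P values carry no descriptive label.

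All of that is correct as description. It does not show that following the plan would produce a wrong result. The 80% carries its within-treatment qualifier in the Synopsis, Protocol 12.1 and SAP 7.2, it matches an output the SAP produces, and no passage claims a power against placebo. The option to stop enrolment protects power only in sequences 1 and 2, which itself tells the reader where the priority lies. The sentence about sufficient data covers efficacy, safety and PK together and is not a power statement.

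On the P values, the objective is worded against placebo, the SAP reports that contrast, and nothing says VX-371 alone will be judged on its within-treatment change. The antibiotic argument illustrates why an uncontrolled change is weak evidence, but it cannot be given a size. The documents state neither the share of subjects who cycle nor the shift to expect, and subjects on continuous alternating regimens have no off-cycle.

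**Conclusion.** No change follows. Both stated powers are right (81.2% and 80.3% recomputed), and what is missing is a power figure for one secondary comparison in a Phase 2a trial. That power is about 51% to 52% for 3 points, assuming SD 7 per change, no between-period correlation and 45 completers. It would be 55% to 80% if the correlation were 0.1 to 0.5. Zero correlation is the cautious end of that range, and Protocol 8.2.1 itself expects the within-subject comparison to add power.

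Modest precision here is a fair trade-off for putting two thirds of the subjects (100 of 150) on the primary question. The planned CI, about plus or minus 3.0 points at this variance, will show readers how much the VX-371-alone comparison can support. A statistician writing the report would read the within-treatment P values as uncontrolled and rest any statement about VX-371 alone on the placebo difference. A sentence giving the lower power would be a courtesy to the reader; it would alter no analysis, estimate or conclusion.

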## 12.2 Analysis Sets

The All Subjects Set is defined as all subjects who were randomized or have received at least 1 dose of inhaled study drug (i.e., all subjects in the study). All subject data listings will be referenced using the All Subjects Set, unless otherwise specified.

The Full Analysis Set (FAS) is defined as all randomized subjects who carry the intended homozygous *F508del-CFTR* mutation and have received at least 1 dose of inhaled study drug. The FAS is to be used in efficacy analyses in which subjects will be analyzed according to the treatment sequence to which they were randomized. All analyses of background data and efficacy data will be based on the FAS.

The Safety Set is defined as all subjects who received at least 1 dose of inhaled study drug. All analyses of safety data will be based on the Safety Set. Subjects will be analyzed according to the treatment sequence received.

## 12.3 Statistical Analysis

The primary objective of this study is to evaluate the safety and efficacy of treatment with VX-371 in HS compared to HS alone treatment in subjects with CF who are homozygous for the *F508del-CFTR* mutation and being treated with Orkambi.

This section presents a summary of the planned statistical analyses of efficacy and safety for this study. The Vertex Biometrics department or a designated CRO will analyze the data derived from this study. SAS® Version 9.2 or higher will be used to generate all statistical outputs (tables, figures, listings, and data sets).

Statistical analysis and presentation details will be provided in the SAP for the study.

### 12.3.1 General Considerations

All individual subject data for those randomized or exposed to inhaled study drug will be presented in data listings.

**Continuous variables** will be summarized using the following descriptive summary statistics: number of subjects (n), mean, SD, standard error (SE), median, minimum value (min), and maximum value (max). The precision of the measurement for each continuous variable will be specified in the SAP.

**Categorical variables** will be summarized using counts and percentages. Percentages will be presented to 1 decimal place.

**Treatment emergent (TE) period** for Treatment Period 1 will correspond to data from the first dose of inhaled study drug in the first period to the safety evaluation visit (28 days after the last dose in the first period and prior to the first dose of Treatment Period 2). Similarly, the TE period for Treatment Period 2 will correspond to data from the first dose of inhaled study drug in Treatment Period 2 through the Safety Follow-up Telephone Contact, or 28 days after the last dose in the second period for subjects who do not have a Safety Follow-up Telephone Contact.

**Baseline:** For this crossover study, 2 types of baseline will be defined. The **study baseline** is defined as the most recent nonmissing measurement (scheduled or unscheduled) collected before the first dose of inhaled study drug in the study. Study baseline will be used for all summaries of demographics, background, and baseline characteristics as well as all efficacy data analyses, including the primary endpoint analysis. In addition, **period baseline** is defined as the most recent nonmissing measurement (scheduled or unscheduled) collected before the first dose of inhaled study drug in each treatment period. For Treatment Period 2, the baseline value should be from an assessment measured after the TE period for Treatment Period 1. Period baseline will be used for all safety data analyses. For ECG, baseline for Period 1 will be defined as the average of the 3 pretreatment measurements on Day 1.

**Absolute change from study baseline** will be calculated as post-baseline value – study baseline value.

**Absolute change from period baseline** will be calculated as post-baseline value – period baseline value.

### **12.3.2 Background Characteristics**

Subject disposition, demographic and baseline characteristics, prior and concomitant medications, study drug exposure and compliance, and other background characteristics will be summarized. Additionally, all subject data will be presented in subject data listings. All summaries will be based on the FAS unless otherwise specified in the SAP for the study. No statistical hypothesis testing will be performed on background characteristics.

#### **12.3.2.1 Subject Disposition**

The number and percentage of subjects in the FAS will be summarized by treatment sequence in each of the following disposition categories:

- Completed inhaled study drug treatment
- Prematurely discontinued treatment and the reasons for discontinuation
- Last scheduled on-treatment visit completed for subjects who discontinued treatment
- Completed study
- Prematurely discontinued the study and the reasons for discontinuation
- Last scheduled visit completed

#### **12.3.2.2 Demographics, Medical History, and Baseline Characteristics**

Demographic, medical history, and baseline characteristics will be summarized by treatment sequence. Protocol deviations will be provided as a subject data listing only. Important protocol deviations will be summarized.

The following demographics and study baseline characteristics will be summarized by treatment sequence for the FAS: sex, race, ethnicity, age, weight, height, BMI, region, study baseline ppFEV1, [REDACTED].

### **12.3.2.3 Prior and Concomitant Medications**

Medications used in this study will be coded by using the World Health Organization Drug Dictionary - Enhanced and categorized as follows:

- **Prior medication:** any medication that started before the first dose of inhaled study drug, regardless of when it ended.
- **Concomitant medication:** medication continued or newly received during the TE period for Treatment Period 1 or Treatment Period 2.

A given medication can be classified as a prior medication, a concomitant medication, or both prior and concomitant. If a medication has a missing or partial missing start/end date or time and it cannot be determined whether the medication was taken before initial dosing or concomitantly, it will be considered as prior and concomitant.

Prior medications will be summarized by treatment sequence, and concomitant medications will be summarized by treatment based on the FAS.

### **12.3.2.4 Study Drug Exposure and Compliance**

Exposure to study drug (i.e., duration of treatment) will be summarized by treatment for the FAS in terms of duration of treatment a subject received (in days), defined as the last day minus the first day of study drug plus 1 within the Treatment Period.

Study drug compliance will be calculated as follows:

$$100 \times [1 - (\text{Total number of days study drug interrupted}) / (\text{Duration of study drug exposure})]$$

The total number of days of study drug interrupted is defined as the sum of (number of days of study drug interrupted in each interruption interval); where number of days of study drug interrupted in each interval is defined as the interruption end date – the corresponding interruption start date + 1.

Duration of treatment and study drug compliance will be summarized by means of descriptive summary statistics.

